5.3 Exploratory Objectives

- To assess the pharmacodynamics (PD) effect of KY1044 as single agent and in combination with atezolizumab in tumor tissue.
- To assess the PD effect of KY1044 as single agent and in combination with atezolizumab in peripheral blood.
- To determine the level of target occupancy in response to KY1044 as single agent (Phase 1 only).

6.0 Study Design

This study is a first in human, open-label, Phase 1/2, multi-center study consisting of a Phase 1 dose escalation component with KY1044 as single agent and a dose escalation of KY1044 in combination with atezolizumab that will start after at least two cohorts of KY1044 as single agent have been considered to be safe and tolerable.

KY1044 will be administered i.v. every 3 weeks (Q3W). Atezolizumab will be administered according to dosing instructions given in the approved label for marketing (1200 mg i.v. Q3W) until the patient discontinues the study for up to 48 months.

Patients should not discontinue treatment based on progressive disease per response evaluation criteria in solid tumors version 1.1 (RECIST 1.1) (study discontinuation due to progressive disease as per iRECIST) unless clinical deterioration or increase in tumor markers is observed.

Phase 1:

In Phase 1, patients with advanced/metastatic malignancies (all comers) and with preferred indications will be enrolled. Preferred indications are: head and neck squamous cell carcinoma (HNSCC), gastric/esophageal cancer, hepatocellular carcinoma (HCC), non-small cell lung cancer (NSCLC), melanoma, cervical cancer, renal cell cancer, pancreatic cancer and triple negative BC.

Dose escalation part - KY1044 single agent

In the Phase 1 part of the study, cohorts of patients with advanced/metastatic malignancies, preferentially those with indications which are expected to have a high expression of inducible T cell costimulator (ICOS), will be treated with KY1044 as single agent Q3W until the maximal tolerated dose (MTD) is reached or a lower recommended phase 2 dose (RP2D) is established. It is expected that a RP2D based on safety, PK, and PD data may be established before the MTD is reached, as this has been the case with other checkpoint inhibitors.

The dose escalation will be guided by the Modified Toxicity Probability Interval Design (mTPI-2 design, Guo et al 2017 (1)), which is an adaptive dose-finding method that allows dose escalation and de-escalation according to the pre-calculated decision table in Appendix 14.1 of the SAP. The maximum sample size for dose escalation in each Phase 1 component (single agent and combination therapy) will be 36 patients, using cohorts of a minimum of three patients (Section 4.1.1 of the protocol).

Dose escalation part – KY1044 in combination with atezolizumab

The combination part of the study will commence after at least two cohorts of KY1044 as single agent have been considered to be safe and tolerable and the data suggest that it is reasonable to begin treatment in combination. The combination dose escalation will follow a Q3W dosing schedule. Treatment in combination will escalate until the MTD is reached or a lower RP2D is established based on safety, PK and available PD data. The dose escalation will be guided by the mTPI-2 design, which is an adaptive dose-finding method that allows dose escalation and de-escalation according to the pre-calculated decision table. The maximum sample size for dose escalation will be 36 patients using cohorts of a minimum of three patients.

Phase 1: Enrichment cohorts (optional)

An optional enrichment part may include the testing of additional patients at one or more dose levels to better understand the safety, tolerability, biomarkers, PK, preliminary anti-tumor efficacy and /or PK/PD relationships of KY1044 as single agent and/or in combination with atezolizumab.

The enrichment part of the study will only use doses that have already been explored in the Phase 1 dose escalation part of the study, and have been determined to be safe.

Total number of patients in Phase 1

The total number of patients included across all cohorts in the Phase 1 dose escalation and enrichment parts will be approximately 150.

Phase 2:

In Phase 2, patients will be enrolled

- in one or more specific indication(s), in which efficacy has been observed in Phase 1 to support definition of the RP2D for future indications and
- in tumor indications, where signs of anti-tumor activities were detected during Phase 1 (indications, where complete response (CR), partial response (PR) or durable stable disease (SD) with tumor shrinkage that does not qualify for PR have been observed) and
- in selected indications, HNSCC, NSCLC, gastric/esophageal cancer, cervical cancer,

In the absence of identifying an MTD or single efficacious dose in Phase 1, an initial Phase 2 dose assessment part in one or more specific indication(s) will be opened to compare the efficacy and biomarker readouts of two biologically relevant dose levels of KY1044 (as single agent or in combination with atezolizumab) in a more homogeneous population. Up to 20 patients (i.e. 15 anti-programmed cell death ligand 1 [PD-(L)1] naïve patients and where feasible five anti-PD-(L)1 pre-treated patients) will be included at each dose level and indication. Together with safety, efficacy and biomarker data from Phase 1, data from this part will assist with the selection of the RP2D. Once the MTD and/or RP2D has been identified, Phase 2 may be extended to explore efficacy at the RP2D in additional selected indications as described below.

KY1044 as Single Agent

A Phase 2 part will be opened should signs of anti-tumor activity (defined as CR, PR or SD with tumor shrinkage that does not qualify for PR) be seen in at least one subject in the Phase 1 dose escalation parts in any indication (in either anti-PD-(L)1 naïve or pre-treated patients). Initially up to 15 anti-PD-(L)1 naïve patients will be enrolled and depending on early efficacy additionally up to 30 patients will be enrolled per each indication. In the anti-PD-(L)1 pre-treated group of patients, initially five patients will be enrolled per indication and depending on early efficacy in these patients, additionally up to 15 patients will be enrolled in certain indications.

KY1044 in Combination with Atezolizumab

Patients will be enrolled in the Phase 2 part in selected indications (HNSCC, NSCLC, TNBC, gastric/esophageal and cervical cancers and any indication showing activity in the Phase 1 dose escalation of the combination) in order to assess preliminary anti-tumor efficacy. These patients will either be

- anti-PD-(L)1 treatment naïve or
- pre-treated with anti-PD-(L)1

In the anti-PD-(L)1 treatment naïve group, initially approximately 15 patients will be enrolled in a defined indication and depending on response rates, certain indications may be further expanded to up to 30 patients.

[figure not shown]
In the anti-PD-(L)1 pre-treated group, initially a minimum of five patients will be enrolled in each of the defined indications which may be further expanded to up to 15 patients, depending on emerging efficacy data.

Should enrolment for any of these disease indications not be feasible, or if the early response assessment (see below) suggests that there is only limited benefit in one or more of these indications, then enrolment to that group may be closed before the target is met.

Early Response Assessment in Phase 2:

The early assessment of objective response rate (ORR) will compare observed response rates to historical controls, to define a minimum number of objective responses (CR, PR or durable SD with tumor shrinkage that does not qualify for PR) per RECIST 1.1 per each indication in the initial Phase 2 phase, in order to decide if enrolment should be further extended up to 40 patients.

6.1 Study Flow Chart

*Note: Additional provisions may be made for patients who are ongoing on treatment and are still receiving clinical benefit at 48 months for continuation of treatment.

6.2 Sample Size Considerations

Phase 1:

A maximum of 36 patients will be used for each Phase 1 dose escalation component (single agent and combination therapy). The total number of patients included across all cohorts in the Phase 1 dose escalation and enrichment parts will be approximately 150.

Phase 2:

The initial Phase 2 dose assessment part in one or more specific indication(s) (Section 3.1.4 in the protocol) will include approximately 20 patients (that is 15 anti-PD-(L)1 naïve and where feasible five anti-PD-(L)1 pre-treated patients) at each of two dose levels of KY1044 (as single agent or in combination with atezolizumab).

Once the RP2D is established, Phase 2 may be extended and approximately 15 patients will be enrolled initially in each tumor type in the anti-PD-(L)1 naïve subgroup per each indication in either the single agent cohort or the combination cohort.

The full sample size of specific indications in Phase 2 of the study will be based on early evaluation of ORRs and only indications with promising response rates will be expanded further (up to 40 per subgroup). The Go-no-go decision criteria for cohort expansion will be based on historical ORR and a target ORR for KY1044 treatment. No formal statistical testing will be performed. Instead confidence intervals will be constructed around the ORR observed in each cohort, and this will enable decisions to be made around the likely success of future studies.

Historical ORR for monotherapy with immune checkpoint inhibitors in the second line metastatic setting are in the region of 15% to 25% for anti-PD-(L)1 inhibitors as monotherapy across the different indications and will be even lower in more advanced stages of disease (\geq 3 lines of anti-cancer treatment in the metastatic setting).

In order to illustrate the impact of sample sizes of 15 or expansion to 40 on the width of the confidence intervals, example evaluations are given for these 3 situations (ORR of 13% (3 and more lines of prior therapies in the advanced metastatic setting and 20% and 33% ORR for 2nd line metastatic setting) for cohort sizes of either 15 or 30 patients are given below:

- If the observed response rate is 13% (2/15), the 2-sided 80% confidence interval will be (4%, 32%).
- If the observed response rate is 20% (3/15), the 2-sided 80% confidence interval will be (8%, 39%).
- If the observed response rate is 33% (5/15), the 2-sided 80% confidence interval will be (17%, 53%).
- If the observed response rate is 13% (5/40), the 2-sided 80% confidence interval will be (6%, 22%).
- If the observed response rate is 20% (8/40), the 2-sided 80% confidence interval will be (12%, 30%).
- If the observed response rate is 33% (13/40), the 2-sided 80% confidence interval will be (23%, 44%).

In the anti-PD-(L)1 pre-treated subgroup, initially five patients will be recruited in each indication in either the single agent cohort or the combination cohort. These patients will have already progressed on previous immunotherapy; hence any individual response would indicate a proof of mechanism in these subject groups. If signs of efficacy have been observed in at least one subject any of these anti-PD-(L)1 pre-treated indications a further expansion up to 15 patients per cohort will be considered.

This number of patients, also offers the opportunity to evaluate further the safety and PK/PD of the chosen MTD/RP2D of KY1044 as single agent or in combination with Atezolizumab.

Overall a maximum of 412 patients may be enrolled into the study (Phases 1 and 2).

6.3 Randomization and Blinding

Not applicable. This is an open-label study without randomization.

7.0 Study Endpoints

7.1 Endpoint Attributes

Objectives	Endpoints	
Primary	Primary Endpoints	
Phase 1:	Phase 1:	
To characterize the safety and tolerability of KY1044 as single agent and in combination with atezolizumab and to identify recommended doses for future studies. Phase 2: To estimate the anti-tumor efficacy of KY1044 as single agent and in combination with atezolizumab.	 Safety: Incidence and severity of adverse events (AEs) and serious AEs (SAEs), including changes in laboratory parameters, vital signs and electrocardiograms (ECGs). Tolerability: Dose interruptions, reductions and dose intensity. The incidence of dose limiting toxicities (DLTs) with KY1044 as single agent during the first 21 days of treatment. The incidence of DLTs with KY1044 in combination with atezolizumab during the first 21 days of treatment. 	
Secondary	ORR per RECIST 1.1. Secondary Endpoints	
 To evaluate the preliminary anti-tumor activity of KY1044 as single agent and in combination with atezolizumab (Phase 1 only). To characterize the safety and tolerability of KY1044 as single agent and in combination with atezolizumab (Phase 2 only). To characterize the PK profile of KY1044 as single agent and in combination with atezolizumab (Phase 2 only). To characterize the PK profile of KY1044 as single agent and in combination with atezolizumab. To assess emergence of anti-KY1044 and anti-atezolizumab antibodies following one or more i.v. infusions of KY1044 single agent and/or in combination with atezolizumab. To assess changes in biomarkers from 	 Efficacy: Best overall response (BOR), Progression free Survival (PFS) and Duration of Response (DOR) per RECIST 1.1. ORR and PFS per immune-related (i) RECIST (Phase 1 and Phase 2). ORR per RECIST 1.1 (Phase 1 only). Survival rate at 12 and 24 months. Safety: Safety: Incidence and severity of AEs and SAEs, including changes in laboratory parameters, vital signs and ECGs (Phase 2). Tolerability: Dose interruptions, reductions and dose intensity (Phase 2). 	

Protocol No: KY1044-CT01	
 predictors of efficacy of KY1044 as single agent and in combination with atezolizumab. To describe the survival rate at 12 and 24 months of patients treated with KY1044 as single agent and in combination with atezolizumab for each disease group. 	 KY1044 PK measures; Serum concentration vs. time profiles. Anti-drug antibodies: Presence and/or concentration of anti-KY1044 and anti-atezolizumab antibodies. Biomarkers: Presence of tumor-infiltrating lymphocytes (TILs) as determined by expression of ICOS, forkhead box P3 (FOXP3) and cluster of differentiation (CD) 8 cells (immunohistochemistry [IHC]).
Exploratory	Exploratory Endpoints
 To assess the PD effect of KY1044 as single agent and in combination with atezolizumab in tumor tissue To assess the PD effect of KY1044 as single agent and in combination with atezolizumab in peripheral blood To determine the level of target occupancy in response to KY1044 as single agent (Phase 1 only) 	 Tumor tissue: Expression of immune- and response related markers such as (but not limited to) PD-L1, CD163, CD68 by IHC. Messenger Ribonucleic Acid (mRNA) gene signature (transcriptomics/ Nanostring) with special interest in IFN gene signature (PanInflammatory panel and/or IO360 panel) Peripheral blood: Peripheral, soluble ligands and cytokine levels (e.g., interferon gamma [IFNγ] tumor necrosis factor alpha [TNFα], granulocyte-macrophage colony-stimulating factor (GM-CSF)) contingent on availability of assay (i.e. SIMOA). Phenotype and markers of immune cells (IC) activation in peripheral blood . Plasma and peripheral blood . Plasma and peripheral blood mononuclear cells (PBMCs) gene signature (ribonucleic acid, RNA) (transcriptomics/Nanostring). ICOS receptor occupancy (RO) in PBMCs (KY1044 as single agent in Phase 1 only)

7.2 Analysis Sets

The following analysis sets will be used for presentation of the data.

For each analysis set, the number and percentage of patients eligible for inclusion will be summarized. A listing of reasons for exclusion from analysis sets will be provided by subject.

A subject data-listing of subject analysis set will be provided.

7.2.1 Screened Set

The patients who have signed informed consent form will be considered as screened subject.

7.2.2 Enrolled Analysis Set

The patients from screened set who have been allocated to study drug regardless of whether the study drug was received or not will be included in enrolled set.

7.2.3 Full Analysis Set

The full analysis set (FAS) will consist of all patients who are allocated to study drug, regardless of treatment ultimately received. Patients will be grouped according to the study drug they will be allocated to. The FAS will be the primary analysis set for efficacy endpoints.

7.2.4 Safety Analysis Set

The safety set will consist of all patients who take at least one dose of study drug within the relevant phase. Patients will be grouped according to the study drug received at cycle 1 day 1. The safety set will be the analysis set used for safety endpoints.

7.2.5 Dose Limiting Toxicity Evaluable Set

The DLT evaluable set will be patients who have been on study for 1 full cycle (21 days) and have received adequate treatment with KY1044 as single agent or in combination with atezolizumab (i.e. have had full infusion of planned doses of KY1044 and Atezolizumab if appropriate) or have experienced a DLT in Cycle 1. The evaluation of DLTs in Phase 1 of the study will occur in this population.

7.2.6 Pharmacokinetic Evaluable Set

The PK evaluable set will consist of all patients who had sufficient concentration-time data within the relevant phase to permit calculation of PK parameters for KY1044. For patients who were noncompliant with respect to administration of KY1044, or for patients with incomplete data, a decision as to their inclusion in the PK analysis will be made on a case-by-case basis. The PK evaluable set will be used for evaluation of PK parameters.

7.2.7 Anti-Drug Antibody Evaluable Set

The anti-drug antibody (ADA) evaluable set will consist of all patients who receive at least one dose of KY1044 or atezolizumab and have ADA results available for analysis within the relevant phase. This population will be used for the analyses of anti-KY1044 and anti-Atezolizumab antibodies.

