# Property of the Sanofi Group - strictly confidential

# 2.1.2 Secondary Objectives

- To evaluate the preliminary anti-tumor activity of KY1044 as single agent and in combination with atezolizumab (Phase 1 only)
- To characterize the safety and tolerability of KY1044 as single agent and in combination with atezolizumab (Phase 2 only)
- To characterize the PK profile of KY1044 as single agent and in combination with atezolizumab
- To assess PK of atezolizumab in combination with KY1044
- To assess emergence of anti-KY1044 and anti-atezolizumab antibodies following one or more IV infusions of KY1044 single agent and/or in combination with atezolizumab
- To assess changes in biomarkers from baseline in tumor tissue as potential predictors of efficacy of KY1044 as single agent and in combination with atezolizumab
- To describe the survival rate at 12 and 24 months of patients treated with KY1044 as single agent and in combination with atezolizumab for each disease group

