# 4.3 Exclusion Criteria

Patients eligible for this study must not meet any of the following criteria:

- 1. Presence of symptomatic CNS metastases, or CNS metastases that require local CNS-directed therapy (such as radiotherapy or surgery), or increasing doses of corticosteroids within the prior 2 weeks of first dose of study treatment. Patients with treated brain metastasis, unless neurologically stable (for 4 weeks post-treatment and prior to study enrolment) and off of steroids for at least 2 weeks before the first dose of study treatment
- 2. History of severe hypersensitivity reactions to other mAbs and/or their excipients
- 3. Known presence of neutralizing anti-atezolizumab antibodies (for patients previously treated with atezolizumab)
- 4. Having out of range laboratory values defined as:
  - Creatinine clearance or glomerular filtration rate ≤30 mL/min estimated by the Cockroft-Gault (C-G) or other medically acceptable formulas such as MDRD (Modification of Diet in Renal Disease) or CKD-EPI (the Chronic Kidney Disease Epidemiology Collaboration)
  - Total bilirubin >1.5 x Upper Limit of Normal (ULN), except for patients with Gilbert's syndrome who are excluded if total bilirubin >3.0 x ULN or direct bilirubin >1.5 x ULN
  - ALT >3 x ULN, except for patients that have tumor involvement of the liver, who are excluded if ALT >5 x ULN
  - AST >3 x ULN, except for patients that have tumor involvement of the liver, who are excluded if AST >5 x ULN
  - Absolute neutrophil count (ANC)  $<1.0 \times 10^{9}/L$
  - Platelet count  $<75 \times 10^9/L$
  - Hemoglobin <9 g/dL
- 5. Impaired cardiac function or clinically significant cardiac disease, including any of the following:

- Clinically significant and/or uncontrolled heart disease such as congestive heart failure requiring treatment (New York Heart Association (NYHA) Grade ≥2), uncontrolled hypertension or clinically significant arrhythmia
- QTcF >470 msec on screening ECG using Fridericia's formula (QTcF) or congenital long QT syndrome
- Acute myocardial infarction or unstable angina pectoris <3 months prior to first dose of study treatment

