#### 6.4.2 Pharmacokinetic and Anti-drug Antibody Sampling Schedule

Serum concentrations of KY1044 and atezolizumab and detection of ADA will be assessed from blood samples taken during the study using validated bioanalytical methods. Assay methodologies and procedures will be described in analytical plans to be finalized before the start of sample analysis.

Multiple samples for concentration-time profiles for KY1044 will be taken in Cycles 1, 3 and 6 (see Table 6-5, Table 6-6, Table 6-7). For other cycles, samples will be taken for KY1044 serum concentrations and for atezolizumab serum concentrations at each cycle pre-infusion, end of infusion, End of Treatment and End of Study.

Anti-Drug Antibody samples will be drawn pre-infusion at all cycles and at the End of Study.

Samples will be collected at the timepoints specified in Table 6-5, Table 6-6, Table 6-7. Tolerances for deviation from the nominal time of sampling are provided in the tables below. These tolerances indicate the best time to allow interpretation of data. However, samples taken outside these tolerances will be evaluated so should be taken. The exact date and time of sampling will be recorded. Samples may also be drawn for serum concentration and/or ADA, with prior agreement with the Sponsor, at unscheduled times. Additionally, these blood samples may be used for *ad hoc* biomarker analysis (ie, safety and efficacy analyses).

Cycle	Day relative to most recent infusion	Scheduled timepoint and tolerance
Phase 1		
1	1	Pre-infusion of Cycle 1
1	1	End of KY1044 infusion (up to 5 min delay allowed) a
		1.5 h post-infusion start (±5 min) a
		2.5 h post-infusion start (±5 min) a
		8 h post-infusion start (±1 h) a
1	2	24 h post-infusion start (±2 h)
1	8	168 h post-infusion start (±8 h)
1	11	240 h post-infusion start (±24 h)
1	15	336 h post- infusion start (±24 h)
2	1	Pre-infusion of Cycle 2 (up to 24 h before 2 nd infusion)
		End of KY1044 infusion (up to 5 min delay) a
3	1	Pre-infusion of Cycle 3 (up to 24 h before 3 rd infusion)
		End of KY1044 infusion (up to 5 min delay) a
		1.5 h post-KY1044 infusion start (±5 min) a
3	8	168 h post-KY1044 infusion start (±8 h)
3	11	240 h post-KY1044 infusion start (±24 h)
3	15	336 h post-KY1044 infusion start (±24 h)
4	1	Pre-infusion of Cycle 4 (up to 24 h before 4 th infusion)
		End of KY1044 infusion (up to 5 min delay) a

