5.2 Secondary Objectives

- To evaluate the preliminary anti-tumor activity of KY1044 as single agent and in combination with atezolizumab (Phase 1 only).
- To characterize the safety and tolerability of KY1044 as single agent and in combination with atezolizumab (Phase 2 only).
- To characterize the pharmacokinetic (PK) profile of KY1044 as single agent and in combination with atezolizumab.
- To assess emergence of anti-KY1044 and anti-atezolizumab antibodies following one or more intravenous (i.v). infusions of KY1044 as single agent and/or in combination with atezolizumab, respectively.
- To assess changes in biomarkers from baseline in tumor tissue as potential predictors of efficacy of KY1044 as single agent and in combination with atezolizumab.
- To describe the survival rate at 12 and 24 months of patients treated with KY1044 as single agent and in combination with atezolizumab for each disease group.

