10.6.2 Anti-drug Antibody Analysis

The anti-drug antibody analysis will be performed on anti-drug antibody evaluable set.

The anti-drug antibody results will be analyzed descriptively for patients who develop detectable anti-KY1044 and anti-atezolizumab antibodies. The titer of anti-KY1044 and anti-atezolizumab antibodies will be summarized using summary statistics (n, mean, STD, median, minimum and maximum values). The presence of anti-KY1044 and anti-atezolizumab antibodies will be summarized using frequency counts and percentage.

The mean (±STD) plot of titer values of anti-KY1044 and anti- atezolizumab antibodies will be presented.

The summary of anti-KY1044 antibodies incidence will be presented.

The by-subject data listing will be presented.

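### The ADA evaluable set admits patients with only a pre-dose sample, and ADA presence and incidence are not defined against baseline, so the reported percentage need not measure emergence after treatment

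*SAP*

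**What the plan says.** - **Objective.** Protocol 2.1.2 reads "To assess emergence of anti-KY1044 and anti-atezolizumab antibodies following one or more IV infusions of KY1044", alone or with atezolizumab. SAP 5.2 says the same.
- **Analysis set.** SAP 7.2.7 takes patients who "receive at least one dose of KY1044 or atezolizumab and have ADA results available for analysis within the relevant phase". The one set serves both drugs: "This population will be used for the analyses of anti-KY1044 and anti-Atezolizumab antibodies".
- **Summary.** SAP 10.6.2 runs the ADA analysis on that set and states: "The presence of anti-KY1044 and anti-atezolizumab antibodies will be summarized using frequency counts and percentage". It also speaks of patients who *develop* antibodies and announces an *incidence* summary for anti-KY1044. Neither word is tied to baseline, and no incidence summary is named for anti-atezolizumab.
- **Sampling.** Protocol 6.4.2: "Anti-Drug Antibody samples will be drawn pre-infusion at all cycles and at the End of Study". Table 6-7 starts with the Cycle 1 pre-infusion sample and ends with the visit 90 days after the last dose. It allows unscheduled samples but has no end-of-treatment row, whereas the PK tables (6-5 and 6-6) do.
- **Prior exposure.** Protocol 4.2 allows earlier anti-PD-(L)1 therapy. Protocol 4.3 excludes only "Known presence of neutralizing anti-atezolizumab antibodies (for patients previously treated with atezolizumab").

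**The concern.** A percentage meant to answer a question about emergence needs a denominator of patients in whom emergence could be observed, and a numerator that separates new or boosted antibodies from those already there. The plan secures neither.

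The two gaps pull in opposite directions and need not be equal across groups. Early drop-out adds patients with no post-dose sample. Earlier atezolizumab can add patients who are already positive. If either varies by dose level or by treatment history, ADA percentages cannot safely be compared across those groups.

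Planned groups are small. One patient classified differently moves the percentage by 1/15 = 6.7 points in a cohort of 15 and by 1/5 = 20 points in a cohort of 5. The tables may also be acted on: Protocol 9.4.4 allows further PK modelling if concentration or ADA tables hint at an interaction between the two drugs.

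**Working it through.** The documents state no ADA rate, sample size or precision target, so there is no figure to reproduce. The check is textual, with an illustration.

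**1. Can a patient be in the set without a post-dose result?** Yes. SAP 7.2.7 asks for one dose and ADA results, and the Cycle 1 pre-infusion sample is an ADA result. Take a patient who stops after one dose, has no Cycle 2 pre-infusion sample, does not reach the 90-day visit and has no unscheduled sample. That patient has a pre-dose result only and still qualifies. Such loss is plausible: Protocol 4.2 requires a life expectancy above 12 weeks (12 x 7 = 84 days), and the visit falls 90 days after the last dose. With no imputation (SAP 8.9), this patient can never contribute an emergent case.

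**2. Does the plan elsewhere require data that can show the outcome?** Yes. SAP 8.2 needs both a baseline and a post-baseline value for a change. SAP 7.2.5 needs a full cycle with adequate dosing, or a DLT. SAP 7.2.6 needs enough data to calculate PK parameters. SAP 8.8.2 counts a pre-existing adverse event as treatment-emergent only if it worsens. The ADA set and summary have no counterpart.

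**3. How is a pre-dose positive counted?** Neither document says. SAP 8.1 defines baseline in general but is not linked to ADA status. Treatment-induced and treatment-boosted ADA are not defined.

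**4. Denominator effect alone.** Let u be the share of the set with no post-dose sample. With no pre-dose positives, reported percentage = (1 - u) x emergent percentage, so the relative understatement equals u. For an assumed u of 10% to 30%, that is 10% to 30%. Example: 20 in the set, 6 without a post-dose sample (u = 6/20 = 30%), 2 converters. Reported 2/20 = 10%; among those observed, 2/14 = 14.3%.

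**5. Both effects, if pre-dose positives are counted.** Same 20 patients, now with 2 positive before dosing as well as the 2 converters. Reported (2 + 2)/20 = 20%. Emergent: 2/14 = 14.3% among all with a post-dose sample, or 2/12 = 16.7% if the 2 pre-dose positives are among those 14 and are removed.

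**6. Range.** Let b be the share positive pre-dose, m the share of baseline-negative patients with no post-dose sample, and e the induced rate among baseline-negative patients with a post-dose sample; boosted cases are ignored. Then, if pre-dose positives count:

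reported = b + (1 - b)(1 - m)e

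All inputs are assumed.

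| e | b | m | Reported | Difference from e |
|---|---|---|---|---|
| 10% | 0 | 20% | 8.0% | -2.0 points |
| 10% | 10% | 0 | 19.0% | +9.0 points |
| 0% | 10% | any | 10.0% | +10.0 points |
| 30% | 0 | 20% | 24.0% | -6.0 points |

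Over e = 0 to 30%, b = 0 to 10% and m = 0 to 20%, the difference runs from -6.0 to +10.0 points.

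**The case against.** The strongest reply is that SAP 10.6.2 is silent on baseline rather than wrong about it. It does not say that pre-dose positives count, nor whether presence is tabulated per patient or per visit. A per-visit table would show baseline prevalence in its Cycle 1 row and use visit denominators. The words *develop* and *incidence* suggest that emergence was intended. This stands, so the inflation argument is conditional. It does not remove the gap: two programmers could produce different tables from the same text, and the membership rule in 7.2.7 is explicit.

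Second, presence is the protocol's own endpoint (Protocol 2.2.2 and 9.4.2.2), so the mismatch with the objective begins there. That is correct, but the SAP is the place to resolve it.

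Third, prior exposure is a narrow mechanism. KY1044 is first-in-human, so earlier treatment with it cannot explain pre-dose anti-KY1044 positives. Anti-atezolizumab samples are scheduled only for combination patients, and many pre-treated patients may have had a different anti-PD-(L)1 agent. This also stands. A reader might infer that the naive versus pre-treated comparison is distorted for both antibodies; the documents support that possibility only for anti-atezolizumab antibodies in combination patients previously given atezolizumab.

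Fourth, the endpoint is descriptive, titres are summarised and a by-subject listing is planned, so emergent status could be worked out afterwards. That lowers the stakes, but the tabulated percentage is what will be read.

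**Conclusion.** The denominator point holds on the text: SAP 7.2.7 admits patients who could not show emergence, and they dilute any per-patient percentage computed on the set. The numerator point holds as a missing definition: presence and incidence are not related to baseline, and if pre-dose positives are counted the anti-atezolizumab percentage is the one mainly at risk.

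A reader might go further and say that the SAP ignores baseline, or that the secondary objective cannot be answered. The documents do not support either. The plan is silent on baseline, part of its wording leans toward emergence, and the scheduled samples allow the right quantity to be derived.

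The size is unknown. How many patients will have only a pre-dose sample, and how many will be positive before dosing, appears nowhere in the documents. The 20% against 14% or 17%, and the -6 to +10 points, illustrate assumed shares and do not estimate bias.

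**What to change.** **SAP 7.2.7.** Define the set separately for each drug: patients who received at least one dose of that drug and have at least one post-dose ADA result for it. Do not also require a baseline result, since that would discard patients with usable post-dose data. Splitting by drug matches Table 6-7.

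**SAP 10.6.2.** Report treatment-emergent ADA incidence for both drugs and state each denominator:
- induced: baseline negative or missing, then positive post-dose;
- boosted: baseline positive, with a titre rise beyond a threshold taken from the assay validation (these documents give no basis for setting it).

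Report baseline prevalence separately, among patients with a baseline sample.

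**Cost.** A text change before database lock, using samples already scheduled, and a slightly smaller denominator.
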